6.5.1. Disease modifying therapies for MS

Disease modifying therapies (DMTs) are defined as therapies which can favorably alter the course of the disease by reducing the rate and severity of relapses or delaying disease progression by preventing accumulation of disability. Previously, DMTs were identified on an ingredient level, using CM.CMINGL (Ingredients List) in SUPPCM. In the current SDTM, ingredients are listed under CM.CMDECOD and selected if they contain any of the text indicated in Table 11 below. Medications in ATC class S (sensory organs, i.e., ophthalmologicals and / or otologicals) will not be considered. The list in Table 11 will be updated periodically as new DMTs become available.

•••					
ALEMTUZUMAB	MITOXANTRONE				
AZATHIOPRINE	MYCOPHENOLIC ACID				
CERALIFIMOD	NATALIZUMAB				
CICLOSPORIN	OCRELIZUMAB				
CLADRIBINE	OFATUMUMAB				
CYCLOPHOSPHAMIDE	OZANIMOD				
DACLIZUMAB	PEGINTERFERON BETA-1A				
DIMETHYL FUMARATE	PLOVAMER				
FINGOLIMOD	PLOVAMER ACETATE				
GLATIRAMER ACETATE	RITUXIMAB				
INTERFERON BETA-1A	SECUKINUMAB				
INTERFERON BETA-1B	TERIFLUNOMIDE				
LAQUINIMOD	SIPONIMOD				
METHOTREXATE	IMMUNOGLOBULINS NOS				
INTERFERON ALFA	ETRASIMOD				
VUMERITY	BAFIERTAM				
PONESIMOD	DIROXIMEL FUMARATE				
DMTs will be classified as previous or concomitant as defined in Section 6.5.					

Table 11: Disease-modifying therapies for MS

Previous and concomitant therapies (relative to first dose of ponesimod) are summarized for the PAS, by therapeutic organ class and preferred term.

For study reporting purposes, all previous and concomitant therapies are reported in the subject listings for AP3 on the PAS. Therapies are flagged to indicate whether they are previous, concomitant, or post-treatment.

Previous and concomitant DMTs are reported separately and summarized by therapeutic organ class and preferred term as described above for previous and concomitant therapies.

6.6. Appendix 6 Medical History

Medical history was primarily collected and reported in the core study and is therefore stored in SDTM201.MH. Additional medical history collected that was collected during the extension study is stored in SDTM202.MH.

Additional medical history collected in the extension study is listed on the PAS.

6.7. Appendix 7 Laboratory marked abnormalities

Parameter (SI unit)	LL	LLL	HH	HHH
Hemoglobin (g/L)	< 100	< 80	Increase in > 20 g/L above ULN or above baseline (if baseline is above ULN)	Increase in > 40 g/L above ULN or above baseline (if baseline is above ULN)
Hematocrit (L/L)	< 0.28 (female) < 0.32 (male)	< 0.20	> 0.55 (female) > 0.60 (male)	> 0.65
Platelet count (10 ⁹ /L)	< 75	< 50	> 600	> 999
WBC count $(10^9 / L)$	NA	< 1.9	> 20.0	>100.0
Lymphocyte (10 ⁹ /L)	ND	< 0.2	> 4.0	> 8.0
Neutrophils (10 ⁹ /L)	< 1.5	< 1.0	ND	ND
Eosinophils (10 ⁹ /L)	ND	ND	> 5.0	ND
Polymorphonuclear leucocyte/Band cells (%)	ND	ND	> 90%	> 95%
AST (U/L)*	ND	ND	\geq 3 ULN	\geq 5 ULN
ALT (U/L)*	ND	ND	\geq 3 ULN	\geq 5 ULN
Total bilirubin (umol/L)	ND	ND	\geq 2 ULN	\geq 5 ULN
Alkaline Phosphatase (U/L)	ND	ND	> 2.5 ULN	> 5 ULN
INR*	ND	ND	> 1.5 ULN	> 2.5 ULN
Creatinine (umol/L)*	ND	ND	>1.5 ULN or >1.5 x baseline	> 3 ULN or >3 x baseline
Creatinine clearance (mL/min)	< 60	< 30	ND	ND
Urea (mmol/L)	ND	ND	> 2.5 ULN	> 5 ULN
Albumin (g/L)	< 30	< 20	ND	ND
Glucose (mmol/L)	< 3.0	< 2.2	> 8.9	>13.9
Potassium (mmol/L)	< 3.2	< 3.0	> 5.5	> 6.0
Sodium (mmol/L)	ND	< 130	> 150	> 155
Calcium (mmol/L)	< 2.0	< 1.75	> 2.9	> 3.1
Triglyceride (mmol/L)	ND	ND	> 3.42	> 11.4
Cholesterol (mmol/L)	ND	ND	> 7.75	> 12.92

Table 12: Thresholds for marked laboratory abnormalities

* HH and HHH based on CTCAE 2010 v4.03. ALT = alanine aminotransferase; AST = aspartate aminotransferase; ND = not defined; may be complemented by definitions provided by the central laboratory (see central laboratory manual); ULN = upper limit of normal.

Source: Protocol AC-058B301, Appendix 6.

6.8. Appendix 8 Adverse Events of Special Interest

Adverse events of special interest (AESIs) include the anticipated risks of treatment with ponesimod and events that may be related to MS co-morbidities.

The definitions for AESIs are based on the systematic approach using Standardized MedDRA Queries (SMQ). The additional relevant terms can be added to the search or deleted appropriately providing the rationale for the change. The proposal is based on MedDRA version 26.0. The following safety areas are addressed by the pre-defined AESIs:

The following categories for adverse events of special interest (AESI) are defined:

- Bradyarrhythmia occurring post-first dose
- Macular edema
- Bronchoconstriction
- Severe liver injury
- Serious opportunistic infections including PML
- Skin cancer
- Non-skin malignancy
- Convulsions
- Unexpected neurological or psychiatric symptoms/ signs (PRES, ADEM, atypical MS relapses)

Infection related AEs are identified by the AEs belonging to the MedDRA system organ class (SOC) "Infections and Infestations" (primary SOC), only if reported as serious or severe. If the intensity information is missing, the AE is conservatively considered to be of severe intensity.

See below for the search criteria (based on preferred terms and/or standardized MedDRA queries) used for pre-defined AEs to be included in the above safety areas of special interest.

The time to first treatment-emergent AESI in AP3 for each AESI category (in days) is defined as [date of first treatment-emergent AE in AESI category – ponesimod start date + 1] in days. If first treatment-emergent AE in AESI category is after the restart of treatment after pregnancy interruption period, then the time to first treatment-emergent AESI in AP3 (in days) is defined as: [date of first treatment-emergent AE in AESI category – ponesimod start date + 1 – (end of pregnancy interruption – (start of pregnancy interruption + 15) + 1)]

Subjects without any treatment-emergent AEs in a given AESI category during AP3 are censored, and censored time is defined as (the minimum of [last administration of ponesimod in AP3 +15 days, last study date] – ponesimod start date + 1. For subjects with pregnancy interruption: the minimum of [last administration of ponesimod in AP3 +15 days, last study date] – ponesimod start date + 1 – (end of pregnancy interruption – (start of pregnancy interruption + 15) + 1)

Statistical Aliarysis Fiall AC-030D202
--

AESI	SMQ	РТ
Bradyarrhythmia occurring post-first dose	Bradyarrhythmias (including conduction defects and disorders of the sinus node function)	Blood pressure ambulatory decreased, Blood pressure decreased, Blood pressure decreased, Blood pressure diastolic decreased, Blood pressure fluctuation, Blood pressure orthostatic decreased, Blood pressure systolic decreased, Bradycardia, Central bradycardia., Chronotropic incompetence, Circulatory collapse, Diastolic hypotension, Electrocardiogram RR interval prolonged, Heart rate decreased, Hypotension, Labile blood pressure, Loss of consciousness, Mean arterial pressure decreased, Orthostatic hypotension, Presyncope, Procedural hypotension, Syncope
Macular edema		Cystoid macular oedema, Diabetic retinal oedema, Macular cyst, Macular hole, Macular oedema, Macular pseudohole, Macular rupture, Papilloedema, Pseudopapilloedema, Retinal oedema
Bronchoconstriction	Asthma/bronchospasm (narrow and broad) Interstitial lung disease (narrow and broad)	
Severe liver injury	Hepatic failure, fibrosis and cirrhosis and other liver damage- related conditions (narrow) Hepatitis, non-infectious (narrow)	

Table 13:AESI, SMQ and PTs

Serious opportunistic infections including PML	Opportunistic infections (narrow)	
Skin cancer	Skin neoplasms malignant and unspecified (narrow and broad)	
Non-skin malignancy	Malignant or unspecified tumours (narrow and broad) excluding the PTs included in the SMQ Skin neoplasms malignant and unspecified (narrow and broad)	
Convulsions	Convulsions (narrow)	
Unexpected neurological or psychiatric symptoms/signs (PRES, ADEM, atypical MS relapses)		Acute disseminated encephalomyelitis, Posterior reversible encephalopathy syndrome, Multiple sclerosis relapse

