5.4.4.4.2. Serious adverse events

The following summaries are presented:

- Treatment-emergent SAEs by SOC and PT (frequency);
- Treatment-emergent SAEs with onset on Day 1 of first ponesimod administration, by SOC and PT (frequency) single table with a column for ponesimod 10 mg only;
- All SAEs by SOC and PT (frequency);
- Treatment-emergent SAEs by SOC and PT (AEs per 100 subject-years).

Separate listings including all SAEs are provided for AP3 on the PAS.

Treatment emergent SAEs with onset of Day 1 of first ponesimod administration, by SOC and PT (frequency) was presented in the Interim Analysis CSR and is not planned to be presented in the Final CSR.

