5.4.4.4.5. Adverse events of special interest

The following summaries are presented:

- Treatment-emergent AESIs by AESI category and PT (frequency);
- Treatment-emergent AESIs by AESI category and PT (AEs per 100 subject-years).

The following additional (frequency) summaries are presented for the AESI category "Effect on heart rate and rhythm AESI (including hypotension)", for AEs relative to first administration of ponesimod:

- AEs by Day and PT, for Days 1-21;
- AEs on Days 1-7 (overall) by PT;
- AEs on Days 8-14 (overall) by PT;
- AEs on Days 15-21 (overall) by PT.

For summaries by Day following first ponesimod administration, subjects are summarized as follows:

- For Days 1-7 all subjects are summarized under ponesimod 10 mg;
- For Days 8-14 subjects randomized to ponesimod 10 mg are summarized under ponesimod 10 mg, whilst subjects randomized to ponesimod 20 mg or ponesimod 40 mg are summarized under ponesimod 20 mg;
- For Day 15-21 all subjects are summarized under their randomized dose.

This reflects the up-titration scheme and the doses that subjects were receiving at the time.

Time to first treatment-emergent AESI is analyzed separately for each AESI category for AP3 on the PAS using the Kaplan-Meier method, as described in for time to first relapse in Section 6.12.2.

A separate listing including all AESIs is provided based for AP3 on the PAS.

The above summary tables for Days 1-7, 8-14 and 15-21 for the AESI category "Effect on heart rate and rhythm AESI (including hypotension)", for AEs relative to first administration of ponesimod were presented in the Interim Analysis CSR. As no new data are expected, this is not planned to be presented in the Final CSR.

Additionally, Time to first treatment-emergent AESI for each AESI category for AP3, using the Kaplan-Meier method, was presented in the Interim Analysis CSR and is not planned to be presented in the Final CSR.

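### The AESI category labelled as serious opportunistic infections is selected without a seriousness condition, and the serious-or-severe infection set defined in SAP 6.8 belongs to no AESI category

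*SAP*

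**What the plan says.** SAP 6.8 (Appendix 8) lists nine AESI categories. One concerns infection: "Serious opportunistic infections including PML". After the list comes a separate sentence: "Infection related AEs are identified by the AEs belonging to the MedDRA system organ class (SOC") for infections and infestations, primary SOC, "only if reported as serious or severe". Missing intensity is taken as severe for this purpose. The section then introduces search criteria, based on preferred terms and/or SMQs, "used for pre-defined AEs to be included in the above safety areas of special interest". Those criteria are in Table 13, whose columns are AESI, SMQ and PT. The opportunistic-infection row contains "Opportunistic infections (narrow") in the SMQ column, an empty PT cell, and nothing else.

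SAP 5.4.4.4.5 plans two main outputs, both organised by category: "Treatment-emergent AESIs by AESI category and PT (frequency") and "Treatment-emergent AESIs by AESI category and PT (AEs per 100 subject-years"). It also plans a listing of all AESIs. The two tables remain in the Final CSR. The AESI outputs that this section drops are the Day 1 to 21 heart-rate summaries and the Kaplan-Meier analyses.

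Seriousness is a stored variable, AESER, and a missing value counts as serious (SAP 5.4.3.7). Intensity is stored as AESEV, and a missing value counts as severe (SAP 5.4.3.3).

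**The concern.** Two things do not fit together. The category label promises serious events, but the only stated selection rule does not look at seriousness. And a second infection set is defined in enough detail to be programmed, with a base SOC, a condition and a missing-value rule, yet no category or table row uses it.

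Long-term safety is the first objective in SAP 1.1, and infection is a named concern in this programme. SAP 1.2.2 links the 40 mg dose possibly to infection-related events, and Protocol 3.6.1 asks for heightened vigilance for opportunistic infections. A reader of the Final CSR will take a line headed as serious opportunistic infections to be a count of serious events. SAP 1 assigns these outputs to a CRO. Its programmers could filter on seriousness, on serious-or-severe, or not at all, and each choice would give a different count under the same heading.

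**Working it through.** The plan states no figure here, so there is nothing to recompute. The check is to set the definitions side by side and follow each type of event through them.

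**Step 1: the opportunistic-infection row.** Take an event whose preferred term is in the narrow SMQ and compare three rules:

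| Event | A: Table 13 as written (SMQ only) | B: 6.8 infection sentence used as a filter | C: what the label says (AESER = Y) |
|---|---|---|---|
| Serious, any intensity | counted | counted* | counted |
| Seriousness missing (treated as serious) | counted | counted* | counted |
| Non-serious, severe | counted | counted* | not counted |
| Non-serious, mild or moderate | counted | not counted | not counted |

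*Only if the primary SOC is Infections and Infestations. The SMQ contents are not in the documents, so it cannot be said whether every narrow term meets this.

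Rule A differs from the label in two rows and rule B in one. Neither rule reproduces the label.

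**Step 2: the serious-or-severe set.** Its base is a SOC, whereas the opportunistic category is based on an SMQ. None of the nine listed categories is a general infection category, and no Table 13 row uses the SOC. Because the AESI tables run by category and PT, a set without a category has no row in them.

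**Step 3: what is shown elsewhere.** SAP 5.4.4.4.2 plans "Treatment-emergent SAEs by SOC and PT (frequency"), the same display per 100 subject-years, all SAEs by SOC and PT, and SAE listings. Serious infections are therefore visible under their SOC. SAP 5.4.4.3.2 plans TEAEs by PT and maximum intensity, so severe infections are visible by PT.

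**Step 4: can the combined count be recovered from those tables?** Not by addition. A subject may have both a serious and a severe infection and would be counted twice. The intensity table also has no SOC subtotal, and a subject with several infection PTs appears under each of them. The planned listing of all AEs would allow a hand count, but no table gives the number.

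**The case against.** The strongest counter-reading is that the infection sentence in 6.8 is itself the missing restriction. It stands between the category list and the search criteria, only one listed category concerns infection, and Table 13 has no column in which a seriousness condition could be entered. On that reading most non-serious events are already removed and the sentence is not orphaned. The text permits this but does not say it. The reading also leaves the mismatch in column B: severe non-serious events would still sit under the label, and the base would change from an SMQ to a SOC. The ambiguity therefore stands, as does a smaller form of the defect.

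Other objections carry weight and limit the point. A reader might infer that serious infections are not tabulated at all. SAP 5.4.4.4.2 shows that they are, by SOC and PT, as frequencies and as rates. A reader might also infer that events are reclassified as serious. They are not: AESER is untouched and the SAE tables do not depend on Table 13, so the problem is confined to the heading of one AESI category. That table shows PTs, and an AESI listing is planned. The outputs are descriptive, all objectives are exploratory (SAP 2), and over-inclusion in a safety table errs on the cautious side.

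A reader may be tempted to attach a multiple to the overcount. Any such figure would be the reciprocal of an assumed serious share, and neither document supplies that share. It would also not carry over to the frequency table, where SAP 5.4.4.2 counts a subject once per grouping term.

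Finally, the category named for severe liver injury is likewise selected by SMQ with no severity condition. Over-capture there cannot be shown without the SMQ contents, and liver severity has its own laboratory threshold tables and eDISH plot (SAP 5.4.5.1). At most the label could be aligned with the search.

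**Conclusion.** The point holds in a limited form. The stated rule for the opportunistic-infection AESI contradicts its label, so non-serious events can be counted under a heading that says serious, in both the frequency table and the rate table. Separately, the serious-or-severe infection set in 6.8 has no AESI output, and the planned tables do not give the combined count.

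No numerical size can be stated. The overcount is zero if every event captured by the narrow SMQ is serious, and it grows as the serious share falls. The documents do not say where in that range the study lies. The conclusion assumes that Table 13 is applied as written; if the 6.8 sentence is applied as a filter, the mislabelling shrinks to severe non-serious events. The SAE tables are unaffected either way. This is worth correcting because the outputs are still planned and the correction is cheap.

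**What to change.** 1. In the opportunistic-infection row of Table 13, add AESER = Y, with missing treated as serious as in SAP 5.4.3.7, and show a second row for opportunistic infections of any seriousness. The alternative is to keep the SMQ search unchanged and remove the word serious from the label in both the list and the table.
2. Add serious or severe infections as its own AESI category, in the list and in Table 13, using the SOC-based definition already in 6.8 with its missing-intensity rule. The alternative is to state which listed category that sentence filters, and to reconcile its SOC base with the SMQ.
3. As an optional wording alignment, make the severe liver injury label and its search criteria agree.

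The cost is a few lines of SAP text and at most two extra rows in the AESI tables. AESER and AESEV are already collected and their missing-value rules already exist, so no new data are needed.

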6.9. Appendix 9 Medications of Special Interest

6.10. Appendix 10 Covid-19 Analyses

This appendix describes the analyses and presentation of immunogenicity and clinical endpoints for objectives related to the assessment of immune response to Covid-19 vaccination in participants in the AC-058B202 study.

Specific objectives are:

- To describe binding antibody concentrations to SARS-CoV-2 S protein as measured by Enzyme-linked immunosorbent assay (ELISA)
- To describe binding antibody concentrations to SARS-CoV-2 N protein as measured by ELISA
- To describe SARS-CoV-2 neutralization as assessed by SARS-CoV-2 neutralization assays VNA (wild-type virus neutralization assay (wtVNA))
- To describe Covid-19 vaccine responders as assessed by binding antibody concentrations to SARS-CoV-2 S protein.
- To describe Covid-19 infection Adverse events (AEs).

6.10.1. Immunogenicity Variables

Patients receiving non-live vaccinations while on study treatment will have 5 mL of blood drawn prior to and at least 3 weeks after vaccination to explore changes in vaccine-specific antibody titers from pre- to post-vaccination.

For Covid-19 vaccination, the following humoral immune response parameters are measured, including titers of neutralizing antibodies, S- and N-ELISA titers, and S- and N-ELISA positivity.

Humoral Assay	Purpose
SARS-CoV-2 binding antibodies to S protein	Analysis of antibodies binding to SARS-
(ELISA)	CoV-2 S protein
SARS-CoV-2 seroconversion based on	Analysis of antibodies binding to SARS-
antibodies to N protein (ELISA)	CoV-2 N protein
SARS-CoV-2 neutralization (wtVNA)	Analysis of neutralizing antibodies to the
	wild-type virus

 Table 14:
 Types of SARS-CoV-2 Antibodies

6.10.2. Analysis of Immunogenicity Related to Covid-19 Vaccination:

6.10.2.1. Analysis related definitions:

Baseline: The baseline for Covid-19 vaccine analyses is defined as the last pre-vaccination assessment. For participants missing a pre-vaccination assessment, summaries will be restricted to post-vaccination results only, where applicable.

Analysis Set: The Covid-19 Vaccinated Set (CVAS) is defined as all subjects in the PAS who reported receiving at least 1 dose of any Covid-19 vaccine.

Covid-19 vaccines are selected from the SDTM.CM data as described in Section 6.5.

First Vaccine Regimen: For each subject, the 1st and 2nd doses of vaccine in the SDTM CM dataset are considered. Definition of 1st Vaccine Regimen for Janssen vaccine: Only the 1st dose is considered.

First Booster: The 1st subsequent dose of vaccine after first vaccine regimen is considered as the First Booster.

Second Booster: The 2nd subsequent dose of vaccine after first vaccine regimen is considered as the Second Booster.

Lymphocyte count linked to a specific vaccination will be determined as the minimum of the last two available values within six months prior to the first vaccination date for a given participant. If only one value is available within this time range, this value will be used. If none is available in the range, the lymphocyte count value corresponding to the particular vaccination will be considered missing. Categories of "Lymphocyte Count < 500 mm³" and "Lymphocyte Count >= 500 mm³" will be used in the analysis.

For the calculation of the geometric mean and its corresponding 95% CI, the arithmetic mean and its corresponding 95% CI are calculated on the log10 transformed values. These values are back-transformed to provide the geometric mean and its corresponding 95% CI.

Responder definition: for S-ELISA, N-ELISA, and wild type VNA assays separately:

A sample will be considered positive if the value is strictly greater than the LLOQ (> LLOQ). A participant will be considered a responder if one of the following conditions is satisfied:

- The baseline sample value is less than or equal to the LLOQ (\leq LLOQ) and the sample of post first vaccine regimen is strictly greater than the LLOQ (> LLOQ)

- The baseline sample value is strictly greater than the LLOQ (> LLOQ) and the sample value of post first vaccine regimen represents an at least 4-fold (\geq 4-fold) increase from the baseline sample value.

Participants with missing pre- or post- first vaccine regimen assessments will not be evaluated for the Responder definition.

Analysis based on BAU/ml: In order to calibrate across different ELISA assays, the WHO has proposed International Standards (WHO IS). The WHO IS assigned unit for quantifying immunoglobulins is BAU/ml. Per Nexelis, the conversion of ELISA units (EU/ml) to BAU/ml is as shown below:

Human SARS-CoV-2 Pre-Spike IgG ELISA

The results generated for the Human SARS-CoV-2 PreSpike IgG ELISA are reported with concentration units in "ELU/mL". When required, a correlation factor of 1/7.9815 [2] will be applied to convert the reported results from ELU/mL to BAU/mL. For example, a sample with reported anti-PreSpike IgG antibody concentration of 7981.5 ELU/mL will have a concentration equivalent to 1000 BAU/mL.

The following formula may be used for converting concentration units from ELU/mL to BAU/mL:

Result (BAU/mL) = Result (ELU/mL) / 7.9815

Human SARS-CoV-2 Nucleocapsid IgG ELISA

The results generated for the Human SARS-CoV-2 Nucleocapsid IgG ELISA are reported with concentration units in "ELU/mL". When required, a correlation factor of 1/10.3383 [3] will be applied to convert the reported results from ELU/mL to BAU/mL. For example, a sample with reported anti-Nucleocapsid IgG antibody concentration of 10338.3 ELU/mL will have a concentration equivalent to 1000 BAU/mL.

The following formula may be used for converting concentration units from ELU/mL to BAU/mL:

Result (BAU/mL) = Result (ELU/mL) / 10.3383

Identification of antibody concentrations related to each vaccination: As the doses are not labeled in the dataset, determination of the vaccination doses will be based on a combined assessment of the Covid-19 vaccination dates, available in the SDTM CM dataset, and the sample collection dates, available in the SDTM IS dataset, as follows:

- The sequence of vaccination and sample collection dates will be ordered.
- The sample preceding the 1st dose will be considered "Pre-1st Vaccination Regimen"
- The sample following the 2nd dose and preceding the 3rd dose will be considered "Post-1st
 Vaccination Regimen", unless the Vaccine Type is "Janssen", in which case, the sample following the 1st dose will be considered "Post-1st Vaccination Regimen".
- The samples preceding and following the 3rd dose will be considered the "**Pre-1**st **Booster**" and "**Post-1**st **Booster**", unless the Vaccine Type is Janssen, in which case the samples preceding and following the 2nd dose will be considered "Pre-Booster" and "Post-Booster".
- If there is only 1 sample between the 2nd dose and the 3rd dose, the "Planned Timepoint" (i.e. TP3-Pre or TP3-Post) will be used to determine whether the sample is "Post-1st Vaccination Regimen" or "Pre-1st Booster Regimen".
- The samples preceding and following the 4th dose will be considered the "Pre-2nd Booster" and "Post-2nd Booster", unless the Vaccine Type is Janssen, in which case the samples preceding and following the 3rd dose will be considered "Pre-2nd Booster" and "Post-2nd Booster". If there is only 1 sample between the 3rd dose and the 4th dose, the "Planned

CONFIDENTIAL - FOIA Exemptions Apply in U.S.

Timepoint" (i.e. TP4-Pre or TP4-Post) will be used to determine whether the sample is "Post-2nd Vaccination Regimen" or "Pre-2nd Booster Regimen".

The samples preceding and following the 5th dose will be considered the "Pre-3rd Booster" and "Post-3rd Booster", unless the Vaccine Type is Janssen, in which case the samples preceding and following the 4th dose will be considered "Pre-3rd Booster" and "Post-3rd Booster". If there is only 1 sample between the 4th dose and the 5th dose, the "Planned Timepoint" (i.e. TP5-Pre or TP5-Post) will be used to determine whether the sample is "Post-3rd Vaccination Regimen" or "Pre-3rd Booster Regimen".

Evidence of Prior Covid-19 infection: a subject is considered to be with evidence of prior Covid-19 infection if any of the following conditions are met:

- Subject has any Covid-19 AE records before first vaccination in SDTM AE dataset.
- Subject has N- and/or S- ELISA positive antibody concentrations prior to first vaccination.

